6.11.2. MD Anderson Symptom Inventory – Brain Tumor Module

6.11.2.1. MDASI-BT Outcome Measures

Patient symptoms will be measured with the self-administered MD Anderson Symptom Index (MDASI-BT) (Armstrong et. al. 2006). The MDASI-BT will be completed at baseline, end of cycle 1 and thereafter every 2 cycles (26 ± 2 days) starting at cycle 2 and after discontinuation of study therapy (Visit 801) during the study.

The MDASI-BT consists of 22 symptom items (13 items of the core MDASI plus 9 items specific to brain tumors) plus 6 interference items, all with 11-point rating scales. The core items are pain, fatigue, nausea, disturbed sleep, distress (emotional), shortness of breath, lack of appetite, drowsiness, dry mouth, sadness, vomiting, difficulty remembering, and numbness or tingling (MDASI1 to MDASI13). The brain tumor specific items (MDABTS1 to MDABTS9)

are weakness on one side of body, difficulty understanding, difficulty speaking, seizures, difficulty concentrating, vision, change in appearance, change in bowel pattern, and irritability. For the 22 symptom items, 0 equals “not present” and 10 equals “as bad as you can imagine” in the last 24 hours. The 6 interference items measures general activity, mood, work, relations with other people, walking, enjoyment of life where 0 equals “did not interfere” and 10 equals “interfered completely”.

The 22 symptom items may also be grouped by their underlying constructs: (1) affect consists of distress, fatigue, sleep, sad, and irritability; (2) cognition comprises of difficulty understanding, remember, difficulty speaking and difficulty concentrating; (3) focal neurologic deficit comprises of seizures, numbness, pain and weakness; (4) treatment-related symptoms such as dry mouth, drowsiness, and appetite; (5) generalized/disease status symptoms such as change in appearance, change in vision, change in bowel patterns and shortness of breath; and (6) gastrointestinal symptoms like nausea and vomiting.

The MDASI-BT will be scored by reporting the individual items and by calculating the means of all symptom items and of all interference items. The means of the core and brain tumor items may be reported separately.

6.11.2.2. MDASI-BT Analyses

The rate of compliance with completing MDASI-BT will be summarized at the group-level at each assessment: prestudy (baseline), end of cycle 1 and thereafter every 2 cycles (26 ± 2 days) starting at cycle 2 and at discontinuation (Visit 801). Compliance is defined as the number of completed questionnaire/number of expected questionnaire to be completed at the time of the study.

For those patients who had completed at least one assessment, descriptive statistics will be provided for the core symptoms, brain tumor symptoms, symptom interference, and symptom groupings (affect, cognition, focal neurologic deficit, treatment-related symptoms, generalized/disease status symptoms, and gastrointestinal symptoms) at each assessment period by treatment arms. This summary will include number of patients in each arm, number of patients with completed questionnaire, mean, standard deviation, median, minimum, maximum scores and change from baseline.

For those patients who completed a baseline and one post-baseline questionnaire, change from baseline on core symptoms, brain tumor symptoms, symptom interference, and symptom groupings will be assessed. Repeated measures ANOVA will be performed to assess the mean differences in change from baseline between treatment arms, adjusting for baseline score if needed. Least squares mean, mean differences, including 95% confidence interval and p-values indicating significant differences between treatment arms will be provided. Plots of mean and standard deviation for core symptoms, brain tumor symptoms, symptom interference, and symptom groupings over time and change from baseline plots will be provided.

The minimally important difference (MID) is used to assess and interpret mean score differences between treatment arms. A minimally important difference of 1.2 (as defined in the MDASI user manual) will be used as a reference in the time to worsening analysis. Data from each treatment

arm will be analyzed using Kaplan-Meier plots with censoring at the last assessment for patients with no worsening. Median time to worsening with 95% confidence interval will be provided. The proportion of patients who experienced a change from baseline score of 1.2 will also be summarized for each treatment arm and compared between treatment arms.

Relationships (predictors or prognostic) among patient-reported symptoms and with other clinical parameters such as performance status, overall survival, and disease assessments (based on MRI) may be explored. MDASI-BT analyses may also be adjusted for neurocognitive function of the patient.

Other exploratory longitudinal analyses may be performed.

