6.1. General Considerations

Statistical analysis of this study will be responsibility of both PharmaNet/i3 (under the direction of Eli Lilly and Company) and Lilly.

Patients from all sites will be pooled for the purposes of analysis. Inference about survival will be made using a Bayesian posterior probability for the superiority of LY2157299 plus lomustine arm survival over lomustine plus placebo arm. The remaining analyses of this study will estimate differences between arms where appropriate, including exploratory analyses. Descriptive statistics by treatment arm will also be provided.

Results of descriptive analyses and estimates from inferential analyses will be presented by treatment arm. For continuous variables, summary statistics will include number of patients, mean, median, standard deviation, minimum, and maximum. Categorical endpoints will be summarized using number of patients, frequency, and percentages. Any missing longitudinal data will not be imputed, rather estimated from an appropriate random mixed effects model. Transformations will be applied where assumptions behind any analysis are better satisfied by data being transformed onto an alternative scale. All results from any of these analyses will be back transformed to the original scale. Alternatively, nonparametric methods will be applied.

Any change to the data analysis methods described in the protocol will require an amendment ONLY if it changes a principal feature of the protocol. Any other change to the data analysis methods described in the protocol or additional exploratory analyses deemed appropriate, and the justification for making the change and additions, will be described and justified in the statistical analysis plan and/or clinical study report. The following terms and data handling conventions will be used in the analysis.

Table JBAL.6.1. Data Definitions and Rules

Term	Definitions or Rule
Entered	Patients who have signed the informed consent document directly.
Screen failures	Patients who have signed informed consent, do not meet eligibility criteria and are not randomized.
Randomized/ Enrolled	Patients who have been assigned to study treatment and but may have not received any study treatment (LY2157299, LY2152799-matched placebo, or lomustine).
Patients on therapy	Patients who have been randomized/enrolled to study treatment and have received at least 1 dose of study treatment (LY2157299, LY2152799-matched placebo, or Lomustine).

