6.4. Multiple Comparisons/Multiplicity

No adjustment for multiplicity is planned for this study. The primary analysis will compare the OS distributions for only LY2157299 plus lomustine and placebo plus lomustine. Comparisons between other treatment arms will secondary or exploratory in nature.

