6.11.1.2. Neurocognitive Analyses

Compliance rate will be calculated as the number of completed or prorated questionnaires divided by the number of expected questionnaires given those that are still on study. For Trail Making Tests A and B, patients with completed and prorated tests will be included in analysis. A test score can be prorated if test was discontinued or maximum time was used due to a neurological difficulty.

Each neurocognitive test will be converted to a standardized score (mean = 0, SD = 1) using published healthy control data. To prorate discontinued Trail Making Tests A and B, the raw scores will be divided by the number of circles correctly completed and then multiplying the resulting "time per circle" figure by 25. [Wefel et. al. 2011; Heaton RK et. al. 2004]. For each neurocognitive test, standardized scores will be summarized at each assessment. Repeated measures ANOVA will be performed for each measure to assess the mean differences in change from baseline standardized scores between treatment arms, adjusting for baseline score if needed. The change in standardized score from baseline will be calculated and using the Reliable Change Index (RCI) [Wefel et. al. 2011], the neurocognitive status over time will be categorized into improved, stable or decline. The RCI is a threshold that measures improvement or decline in neurocognitive function and represents a 90% confidence interval for the difference in raw score between baseline and the next assessment assuming no real change occurred. It is derived as follows:

$RCI = 1.64 (SEdiff)$ where $SEdiff = [2(SEM^2)]^{1/2}$ and $SEM = SD_1[(1 - r_{xy})^{1/2}]$

where $SEdiff$ is the standard error of difference in raw score from baseline to the next assessment, SEM is the standard error of measurement, SD is the standard deviation, and r_{xy} is the test-retest reliability statistic. All derived RCI will be rounded to the nearest whole number and compared with changes from baseline assessments to determine the change in neurocognitive status. Those changes that did not meet the RCI threshold will be considered stable performance. Any changes from baseline neurocognitive status showing improvement or decline will need to be confirmed at the next assessment if available. In the absence of a confirmatory assessment, any sign of improvement or decline in neurocognitive status will be deemed as stable.

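### Baseline adjustment of the MDASI-BT and neurocognitive change scores is left to an undefined *if needed*; always adjusting would be at least as precise and would remove the discretion

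*SAP*

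**What the plan says.** SAP 6.11.2.2 (MDASI-BT) plans a repeated measures ANOVA of mean differences "in change from baseline between treatment arms, adjusting for baseline score if needed". It then promises inferential output: "Least squares mean, mean differences, including 95% confidence interval and p-values indicating significant differences between treatment arms will be provided". The scales concerned are core symptoms, brain tumor symptoms, interference and six symptom groupings. The same section later allows a further optional adjustment, for the patient's neurocognitive function, also without a rule.

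SAP 6.11.1.2 uses the same construction for each neurocognitive measure: mean differences in "change from baseline standardized scores between treatment arms, adjusting for baseline score if needed".

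No other section supplies the missing rule:

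- Protocol 12.2.9.1 and 12.2.9.2 leave further analyses to the SAP.
- SAP 6.2 deals only with exploratory adjustment of efficacy measures.
- SAP 6.1 says "Any missing longitudinal data will not be imputed, rather estimated from an appropriate random mixed effects model", but names no baseline covariate.
- SAP 6.4 states "No adjustment for multiplicity is planned for this study".

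Elsewhere the SAP does list model terms, for delta QT in 6.13.6 and for continuous biomarkers in 6.17.

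**The concern.** The decision to adjust has no criterion and no stated timing, and it affects numbers that will be reported. Three things could follow.

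- **Precision.** If baseline is omitted, the arms are compared on raw change, which in general has a larger variance than the baseline-adjusted comparison.
- **Chance imbalance.** If the arms differ at baseline by chance, raw change carries regression to the mean into the treatment difference. The minimization factors in SAP 5.3 are performance status, age, and primary or secondary glioblastoma. Symptoms and cognition are not among them.
- **Discretion.** With two admissible analyses and no rule, the choice could be made scale by scale across nine MDASI-BT scales and three arms.

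Health outcomes are a stated secondary objective, and Protocol 8.2 says they are needed for Phase 3 design, so the quality of these estimates has a use.

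**Working it through.** **Inputs.** The documents give no SD, correlation, power or sample size for these analyses, so there is no planned figure to reproduce. The numbers per arm and the allocation ratio are redacted. The values of r, the SD and the arm sizes below are therefore assumptions, shown as ranges. From the documents: the analysis set requires a baseline and at least one post-baseline assessment (SAP 6.11), there are several post-baseline visits (SAP 6.11.2.1), and the minimally important difference is 1.2 points (SAP 6.11.2.2).

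**Step 1: variance at one post-baseline visit.** Let s0 and s1 be the baseline and follow-up SDs and r their correlation.

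- Var(change) = s0² + s1² − 2·r·s0·s1
- Var(adjusted) = s1²(1 − r²)
- Difference = (s0 − r·s1)², which is never negative

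Apart from one degree of freedom and the small cost of estimating the slope, adjustment cannot lose precision. With s0 = s1 = s the variances are 2s²(1 − r) and s²(1 − r²), and their ratio is (1 + r)/2.

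**Step 2: mean of m post-baseline visits.** With equal correlation r between all visits and v = (1 + (m − 1)r)/m, the ratio is (v − r²)/(v − 2r + 1).

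| assumed r | variance ratio, 1 visit | CI width ratio, 1 visit | variance ratio, mean of 3 visits |
|---|---|---|---|
| 0.3 | 0.65 | 0.81 | 0.475 |
| 0.5 | 0.75 | 0.87 | 0.625 |
| 0.7 | 0.85 | 0.92 | 0.775 |
| 0.8 | 0.90 | 0.95 | 0.85 |

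So the variance is 10–35% lower at one visit, with a larger gain when visits are averaged. At r = 0.9 the one-visit gain falls to 5%.

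**Step 3: what this means in patients.** Assume SD 2.0, r = 0.5, 1:1 allocation, a true difference of 1.2 points and a two-sided 5% test. The SD of change is 2.0 × √(2 × 0.5) = 2.00; the adjusted SD is 2.0 × √0.75 = 1.73. For 80% power this needs 44 per arm unadjusted and 33 adjusted. With 30 per arm, power is 64% and 77%.

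**Step 4: chance imbalance.** The standard error of a baseline difference, in SD units, is √(1/n1 + 1/n2). This gives 0.26 for 30 vs 30, 0.20 for 37 vs 75 and 0.19 for 40 vs 80. Given a baseline difference d, unadjusted change is shifted by (1 − r)·d. For d of one standard error, the shift runs from 0.2 × 0.19 = 0.04 SD (r = 0.8) to 0.7 × 0.26 = 0.18 SD (r = 0.3).

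**Step 5: type I error.** This was simulated with 40,000 null trials per setting and one post-baseline visit, for arms of 30/30, 30/60 and 40/80 and r of 0.3, 0.5 and 0.7, at a nominal two-sided 5%.

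- Either analysis fixed in advance: 4.9–5.2%.
- The smaller of the two p-values taken: 7.7–8.1% at r = 0.3, 7.2–7.5% at 0.5, 6.8–6.9% at 0.7.
- Adjusting only when a baseline test has p < 0.05: 4.0–4.7%. There is no inflation, but under randomization such a test fires in about 1 trial in 20, so most of the precision gain is lost.

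**The case against.** The strongest reply is that no harm is demonstrated. *If needed* may be settled before unblinding, and either analysis fixed in advance holds its error rate. This stands. A reader might infer that the sponsor plans to choose after seeing results, but the documents say nothing of the kind. The gap is an unstated criterion and time, and 7–8% describes the worst use of it.

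A reader might also infer that confidence intervals and p-values are at stake for cognition. SAP 6.11.1.2 promises none for its repeated-measures model. The p-values mentioned there compare proportions of patients with stable or improved tests, and the neurocognitive progression comparison is a Cox model; neither depends on this covariate choice.

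Nor should the shift in step 4 be read as systematic bias. Under randomization it is conditional on a chance imbalance and averages to zero.

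It is tempting to say that SAP 6.1 already names a mixed model for repeated measures with the needed terms. It names only an unspecified random mixed effects model, as a general rule for missing longitudinal data.

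Finally, a rich model may be hard to support. Protocol Table JBAL.5.1 gives median PFS on lomustine of 1.64 months and 82 days, so later visits may hold few patients. That argues against requiring a baseline-by-visit term, but not against including baseline itself.

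On importance, SAP 6.1 reserves inference for survival, and time to worsening, the Reliable Change Index categories and the Cox analysis are untouched. This limits the weight of the point without removing it.

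**Conclusion.** The point holds as a low-cost improvement to two secondary analyses. Both sections leave baseline adjustment open with no criterion or timing, and the covariate is observed for everyone who contributes a change score. If it is omitted, the variance given up is 10–35% of the change-score variance at one visit, for assumed r of 0.8 down to 0.3 and equal variances. Even the benign reading, adjusting only after a significant imbalance, is inferior to always adjusting.

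The consequence for reported intervals and p-values is explicit for the MDASI-BT; for the neurocognitive tests it concerns the estimated mean differences. The loss is conditional on the unadjusted option being used, and the error inflation on the choice following the results. The values of r, the SD and the arm sizes are assumptions. The primary overall survival analysis and the sample size are not affected.

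**What to change.** In SAP 6.11.1.2 and 6.11.2.2, replace the conditional clause with: *baseline score will always be included as a covariate in the repeated-measures model*. A baseline-by-visit term can be offered as an option where later visits hold enough patients.

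The cost is a wording change in two places and one degree of freedom per model. No extra data are collected and no patients are lost from the analysis.

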6.12. Bioanalytical and Pharmacokinetic/Pharmacodynamic Methods

Several pharmacokinetic (PK) analyses will be conducted to support this study using both noncompartmental and population pharmacokinetic approaches.

Population-based PK analysis will be performed on sparse PK data (LY2157299 measurements from cycle 1) using non-linear mixed effect modeling from validated PK software programs (for example, NONMEM).

Pharmacodynamic (PD) data from all patients undergoing PD assessments will be analyzed. Pharmacodynamic (PD) data will be documented in the study report by dose, exposure, and time from dose.

Exploratory PK/PD analyses will be conducted as data become available to determine the relationship between exposure and PD effect. The PK/PD data will be analyzed using validated software programs (for example, WinNonlin and NONMEM).

The version of any software used for the analysis will be documented and the program will meet the Lilly requirements of software validation.

Lilly Pharmacokineticist will be responsible for these analysis. Details on the analysis can be found in the Pharmacokinetic Plan.

6.13. Safety Analyses

All safety summaries and analyses will be based upon the safety population that includes patients that have received at least one dose of study drug.

Safety data will be listed and summarized with patient counts and percentages in each treatment arm. Details of the analyses are described in the following sections.

6.13.1. Extent of Exposure

The numbers of patients completing each cycle will be summarized for each treatment arm. In addition, descriptive statistics (mean, median, standard deviation, minimum and maximum) for the number number of cycles completed will be presented. A patient is considered having completed a 28 day cycle if they have received at least 10 days and up to a maximum of 14 days of LY2157299 monohydrate or LY2157299 monohydrate-matched placebo therapy in that cycle.

The number of patients with any dose adjustment will be presented for entire treatment period as well as for each cycle. The number of patients with dose reductions, dose delays, or dose omissions will also be summarized for all treated patients per treatment arm, as will the reasons for dose adjustments.

Dose intensity which calculates the amount of drug taken per cycle compared to the dose the patient was initially assigned at the start of the study will be summarized by cycle and treatment arm for LY2157299 and lomustine therapy. LY2157299 and placebo-matched LY2157299 dosing will be captured on CRF based on the protocol schedule of events: Days 1, 3, 7 +/-2, 12 +/-2, and 14 of cycle 1 (these align with PK sample draws at Cycle 1) and Day 1 +/-2, 6 +/-2, and 12 +/-2 of cycle 2 on. The calculations for LY2157299 planned and prescribed cumulative dose and dose intensity are as follows:

Planned cumulative LY2157299 dose (mg):

PLC = number of cycles started multiplied by assigned dose on cycle 1 day 1 multiplied by 14 where 14 is the planned number of dosing days per cycle.

Prescribed cumulative LY2157299 dose (mg):

PRC = sum prescribed doses taken in all cycles

Note: any dose omission, adjustment or early discontinuation in a cycle need to be taken into account in calculating the cumulative prescribed dose. Treatment end date defined as last dose date will estimate the number of doses patient has taken in the discontinued cycle.

Planned cumulative lomustine dose (mg):

PLC = assigned dose on day 7 of cycle 1 multiplied by 6 where 6 is the number of administrations planned for lomustine.

Prescribed cumulative lomustine dose (mg):

PRC = sum prescribed doses taken in all administrations

Note: any dose omission, reduction or early discontinuation from lomustine need to be taken into account in calculating the cumulative prescribed dose.

Dose intensity in percent is then calculated by taking the prescribed cumulative dose divided by planned cumulative dose and multiplied by 100% respectively for both LY2157299 and lomustine.

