9.1. Treatments Administered

The following treatments will be administered in this study:

- LY2157299 Monotherapy:
 - LY2157299 300 mg/day, given orally as three 50-mg tablets BID for 14 days, followed by 14 days of rest, equaling a 28-day cycle.
- LY2157299 plus lomustine therapy:
 - The first lomustine dose will be given as 100 mg/m².
 - Remaining doses (starting with the second lomustine dose) are based on the investigator's discretion and will be given orally once every 6 weeks at 100 to 130 mg/m².
 - LY2157299 300 mg/day, given orally as three 50-mg tablets BID for 14 days, followed by 14 days of rest, equaling a 28-day cycle.
- Lomustine plus placebo therapy:
 - The first lomustine dose will be given as 100 mg/m².
 - Remaining doses (starting with the second lomustine dose) from 100 to 130 mg/m² are based on the investigator's discretion and will be given orally once every 6 weeks..
 - LY2157299 -matched placebo, given orally as 3 tablets BID for 14 days, followed by 14 days of rest, equaling a 28-day cycle.

Lomustine doses should be rounded to the lowest available capsule strength.

Weight is used to determine dose and should be assessed at each cycle, and dose should be recalculated for each cycle.

The investigator or his/her designee is responsible for the following:

- explaining the correct use of the drug(s) and planned duration of each individual's treatment to the patient/site personnel,
- verifying that instructions are followed properly,
- maintaining accurate records of study drug dispensing and collection,
- and returning all unused medication to Lilly or its designee at the end of the study.

Note: In some cases, sites may destroy the material if, during the investigator site selection, the evaluator has verified and documented that the site has appropriate facilities and written procedures to dispose clinical trial materials.

Patients will be instructed to contact the investigator as soon as possible if they have a complaint or problem with the study drug so that the situation can be assessed.

To be considered compliant, the minimum planned treatment of LY2157299 is 10 days and a maximum of 14 days per 28-day cycle and at least cc1% of the allocated LY2157299 prescribed dose has to be administered within each cycle.

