12.2.5. Treatment Compliance

The number of dose omissions, reductions, delays, number of cycles received, and dose intensity will be summarized for all treated patients per treatment arm. Summarized data will be provided for the treatment period.

Treatment compliance within a cycle means that the patient has taken their allocated treatments as prescribed for that cycle (see Section [9.1](#)). (This is distinct from dose intensity which

calculates the amount of drug taken per cycle compared to the dose the patient was initially assigned at the start of the study and is defined in Section 12.2.10).

Treatment compliance information for LY2157299 and placebo will be collected through both pill counts and by the site querying the patient at the end of each cycle for each patient. The number of tablets taken relative to the number expected to be taken will be summarized by cycle and treatment arm.

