5.1. Summary of Study Design

Study JBAL is a 3-arm, randomized, multicenter, global, Phase 2 study of LY2157299 monotherapy or LY2157299 plus lomustine therapy compared to lomustine plus LY2152799-matched placebo therapy in patients with relapsed or progressed GB.

CCI [REDACTED] patients will be entered with the aim of randomizing CCI [REDACTED] patients in a CCI [REDACTED] fashion to LY2157299 monotherapy or LY2157299 plus lomustine therapy or lomustine plus LY2152799-matched placebo therapy. Patients and investigators will be blinded to the LY2157299 or placebo assignment for those patients who receive lomustine. One cycle is defined as 28 days in all treatment arms and constitutes 14 days on/14 days off of LY2157299/LY2157299-matched placebo.

[figure not shown]
In Cycle 1, lomustine will be given after LY2157299 or placebo has been given for 7 days (on Day 7 of Cycle 1). After the first dose, lomustine will then be given once every 6 weeks to those patients assigned to either the LY2157299 plus lomustine or lomustine plus placebo treatment groups. The planned treatment with lomustine will be limited to 6 administrations.

Patients will receive treatment until disease progression, death, or discontinuation occurs. Patients will be followed for OS until death or study closure. Tumor assessments will be conducted at baseline (within 28 days before the first dose of study drug or 14 days prior to enrollment) and at the end of every 2 cycles (Day 26 ± 2) thereafter.

The primary comparison for efficacy is to compare OS between the LY2157299 plus lomustine therapy and lomustine plus placebo therapy. Additional endpoints (eg, PFS, response rate) will be estimated.

Further analyses will be carried out to estimate efficacy and safety endpoints for LY2157299 monotherapy and LY2157299 plus lomustine therapy. This secondary analysis will provide an assessment of whether the monotherapy treatment with LY2157299 is as active as lomustine alone. At the same time, this design will offer additional information whether LY2157299 monotherapy has a toxicity profile that warrants further investigation.

CCI [REDACTED] interim assessments are planned:

The planned duration of the study is CCI [REDACTED] in order to follow all patients for OS. Overall survival will be collected for all patients, including those who started other

therapies after discontinuation from study drug treatment.

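### SAP 6.13.1 measures lomustine dose intensity against a fixed six doses whatever the time on treatment, so the figure mixes doses reached with dose level and contradicts its own per-cycle definition

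*SAP*

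**What the plan says.** SAP 6.13.1 opens with a verbal definition: "Dose intensity which calculates the amount of drug taken per cycle compared to the dose the patient was initially assigned" at study start. It says this will be summarized by cycle and by arm for both drugs. Protocol 12.2.5 uses the same idea ("calculates the amount of drug taken per cycle compared to the dose the patient was initially assigned") and refers to Protocol 12.2.10 for the definition. Section 12.2.10 gives no formula, so SAP 6.13.1 is the only working rule.

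The formulas in SAP 6.13.1 are:
- LY2157299 planned dose: "PLC = number of cycles started multiplied by assigned dose on cycle 1 day 1 multiplied by 14".
- Lomustine planned dose: "PLC = assigned dose on day 7 of cycle 1 multiplied by 6 where 6 is the number of administrations planned for lomustine".
- Lomustine numerator: "any dose omission, reduction or early discontinuation from lomustine need to be taken into account in calculating the cumulative prescribed dose".
- Ratio for each drug: "Dose intensity in percent is then calculated by taking the prescribed cumulative dose divided by planned cumulative dose and multiplied by 100% respectively".

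Early stopping of lomustine therefore lowers the numerator and leaves the denominator untouched. SAP 5.1 has "Patients will receive treatment until disease progression, death, or discontinuation occurs". Protocol 9.1 allows lomustine doses from the second onward to range from 100 to 130 mg/m², and has the dose recalculated from weight at each cycle.

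SAP 6.13.1 also tabulates, by arm and with reasons, how many patients had doses reduced, delayed or omitted. Patients with any dose adjustment are counted by cycle as well.

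**The concern.** One label covers two different quantities. For LY2157299, a patient who takes everything prescribed and then progresses scores 100%. For lomustine, the same patient scores the fraction of a six-dose course that was reached. The lomustine formula is cumulative, so it cannot produce the per-cycle figure that the same section promises.

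Lomustine delivery in the two blinded arms is a natural check on whether adding LY2157299 makes the backbone drug harder to give. That bears on the secondary safety objective. A summary that rises with time on treatment is a poor instrument for it, because a longer-treated arm gains points that can offset real dose cuts. The base is also the first dose as assigned, so permitted escalation and weight change count as over- or under-dosing.

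**Working it through.** The plan states no dose-intensity result, so there is no figure to reproduce. The steps below apply the SAP formula.

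**1. Dose days.** Attachment 1 of the protocol places lomustine at Cycle 1 Day 7, Cycle 2 Day 21, Cycle 4 Day 6, Cycle 5 Day 21, Cycle 7 Day 6 and Cycle 8 Day 21. With 28-day cycles these are days 7, 28+21 = 49, 84+6 = 90, 112+21 = 133, 168+6 = 174 and 196+21 = 217.

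**2. Single patients.** SAP dose intensity = 100 × (sum of doses) / (6 × first dose).
- Full doses, 1 to 6 received: 16.7%, 33.3%, 50.0%, 66.7%, 83.3%, 100%.
- Three doses, the second and third at 70% of the first: (1 + 2 × 0.7)/6 = 40.0%. This exceeds the 33.3% of a patient with two uncut doses. On doses due, the two score 2.4/3 = 80% and 2/2 = 100%.
- Six doses, doses 2 to 6 at 50%: (1 + 5 × 0.5)/6 = 58.3%.
- Six doses, 100 then five at 130 mg/m²: 750/600 = 125%.

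The 70% and 50% levels are those in Table JBAL.9.1. Protocol 9.4.1.1 keeps a haematologic reduction in force for the rest of the study.

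**3. Arm means with no cuts.** Inputs are the lomustine medians for PFS in Table JBAL.5.1: 1.64 months (49.9 days) and 82 days. Assumptions: exponential PFS, on-time dosing, stopping at progression, and patients who start lomustine. The proportion reaching the dose on day t is exp(−ln2 × (t − 7)/median).
- 1.64 months: 1 + 0.558 + 0.316 + 0.174 + 0.098 + 0.054 = 2.20 doses; 2.20/6 = 36.7%.
- 82 days: 1 + 0.701 + 0.496 + 0.345 + 0.244 + 0.169 = 2.955 doses; 2.955/6 = 49.2%.

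Every due dose was given in full, and only about 5% and 17% of starters reach the sixth. If instead everyone randomized is counted as given dose 1, the means are about 35% and 47%.

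**4. Two arms compared.** Suppose every combination patient is cut to 70% from dose 2. Mean dose intensity is then (1 + 0.7 × (mean doses − 1))/6.

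| Combination PFS and stopping rule | Combination, cut | Control, uncut | Combination on doses due (control 100%) |
|---|---|---|---|
| Same median, 1.64 months | 30.7% | 36.7% | 89% |
| Same median, 82 days | 39.5% | 49.2% | 86% |
| 1.5 × 1.64 months, stop at progression | 37.8% | 36.7% | 86% |
| 1.5 × 82 days, stop at progression | 47.0% | 49.2% | 83% |
| 1.5 × 1.64 months, stop at next scan | 45.7% | 49.7% | 80% |
| 1.5 × 82 days, stop at next scan | 53.3% | 60.2% | 79% |

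The third row, for example, has 2.809 mean doses: (1 + 0.7 × 1.809)/6 = 37.8%. Scan rows use Day 26 of every second cycle (days 54, 110, 166, 222), by which 2, 3, 4 and 6 doses are due. The last column is the mean of patient-level ratios, which is how the SAP ratio is built. Pooling doses over patients in the third row would give 81% instead of 86%.

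**The case against.** The best defence is that six doses is the stated intended course, so the share of that course delivered is a legitimate and transparent quantity. That stands for a measure labelled as course completion. It does not rescue one defined in the same section as per-cycle and reported beside an LY2157299 figure built differently.

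A reader might infer more: that the figure simply measures time to progression, that it hides lomustine dose cuts in the combination arm, and that the OS comparison suffers. The documents do not support this.
- The ratio also falls with dose cuts, omissions and stops for toxicity. With equal time on treatment, cuts still lower it (39.5% against 49.2% at 82 days).
- Cuts are not lost from the report, because dose adjustments are tabulated by arm with reasons. Those tables do not give the fraction of due drug delivered, but they do show the cuts.
- Full cancellation depends on the assumptions. It needs a cut to 70% in every patient plus 1.5-fold longer PFS, and it appears only at the 1.64-month median with immediate stopping. In the 82-day case and in both scan-based cases the cut arm still scores lower.
- The primary Bayesian OS model in SAP 6.10.1 does not use dose intensity. SAP 6.10.3 mentions extent of lomustine exposure only as an optional exploratory covariate and does not name the measure.

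A further objection concerns the remedy. If doses counted as due only until lomustine itself was stopped, a patient who gave up lomustine for toxicity after one full dose but stayed on LY2157299 or placebo would move from 17% to 100%. That is right, and the fix below is worded to avoid it.

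**Conclusion.** The point holds as an inconsistency in SAP 6.13.1 that gives a misleading number, and it should be corrected. The lomustine formula contradicts its own verbal definition and is not on the same basis as the LY2157299 formula. Fully dosed arms would average about 37% to 49% if treatment stops at progression, or about 50% to 60% if it stops only at scheduled scans. Both ranges assume exponential PFS at the two historical medians and on-time dosing.

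When one arm is treated longer, the figure blunts a difference in dose reductions. In the 1.5-fold examples, a gap of 14 to 21 points on doses due shrinks to 2 to 7 points, or in one case reverses by about 1 point. Those sizes rest on assumed universal cuts and illustrate the mechanism; they do not forecast the trial. The fault is confined to one descriptive safety summary.

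**What to change.** In SAP 6.13.1, define planned cumulative lomustine dose as the first assigned dose per m² multiplied by the number of six-weekly administrations due until the end of all study treatment (progression, death or discontinuation of study treatment), with a maximum of six. Count as due any dose omitted, delayed, or not given because lomustine alone was stopped for toxicity. Compute the ratio per patient in mg/m², so that weight change drops out.

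Report three separate lines by arm:
- administrations received, out of six, which keeps the course-completion information;
- lomustine discontinuations with reason;
- doses above the first dose level, so that permitted escalation is visible and is not read as making up for reductions.

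Bring the by-cycle wording in the same section into line with the formula. If lomustine exposure is used as a covariate under SAP 6.10.3, name the measure.

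The cost is a wording change and one derived variable from data already collected. No dosing rule, visit or patient number changes.
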